2.3 PROPOSED SUBGROUPS

No subgroup analyses are proposed for this trial. As noted above (2.2, Secondary Objective #4), we will conduct exploratory analyses of potential interacting variables associated with differential (positive) response to the use of the ACC. As exploratory investigations, it is acknowledged that these analyses will likely be underpowered and are hypothesis-generating only.

3.0 STUDY PARTICIPANTS

3.1 INCLUSION CRITERIA

All study participants will be active members of the KPNC health plan, since all recruitment activities and interventions will take place in KPNC medical facilities.

The inclusion criteria for the ACCESS study, and their rationales, are:

1. Age > 18 years	1. Age of consent
2. Intending to undergo elective primary unilateral TKA at the KPNC SLN Medical Center	2. Indication for use of the ACC; study site is KPNC SLN Medical Center
3. Patient ambulates independently	3. Non-ambulatory patients may have atypical postoperative recovery courses

3.2 EXCLUSION CRITERIA

The exclusion criteria for the ACCESS study, and their rationales, are:

1. Patient declines use of ACC	1. Patient not eligible for ACC study arm
2. Surgeon decides that an ACC will not be placed for any reason	2. Patient not eligible for ACC study arm
3. Known hypersensitivity to ropivacaine or any alternative anesthetic for ACC use	3. Patient not eligible for ACC study arm
4. Hypersensitivity or inability to tolerate peri-articular injections of clonidine, epinephrine, bupivacaine and ketorolac	4. Participants in both arms of the trial are required to undergo peri-articular anesthetic injections
5. Any evidence of substance-use disorder in past year	5. Opioid use is a secondary study outcome measure
6. Non-English speaking	6. Study instruments are all in English
7. Failure to complete all baseline study instruments prior to surgery	7. No baseline measurement available for calculating change
8. Requires secondary procedure at time of TKA (e.g., removal of hardware)	8. Complex surgery may cause change in outcome measures independent of study objectives
9. Not intending to use spinal anesthesia for TKA procedure	9. Atypical surgical approach
10. Actively enrolled in KPNC chronic-pain program	10. Opioid use is a secondary study outcome measure
11. Having been prescribed long-acting opioid (e.g., Oxycontin, MS Contin) within 90 days prior to enrollment	11. Pre-surgery major opioid use may complicate measurement of post-surgery opioid use
12. Inability to tolerate any oral NSAID or acetaminophen or any short-acting opioid	12. NSAIDs, acetaminophen, and short-acting opioids are used for analgesia for all participants

These exclusion criteria are established for safety and to ensure consistency in the participant sample.

3.3 RANDOMIZATION

Randomization will be balanced (i.e., using an allocation ratio of 1:1) and blocked (using randomly chosen block sizes of 2, 4, and 6); no stratified randomization will be used.

The randomization list will be generated by [name] (study Biostatistician) using the "ralloc.ado" procedure in Stata (this procedure creates a balanced, blocked, and self-documenting randomization list) (19). The randomization list will then be used by study staff to create a set of sequentially numbered, sealed opaque envelopes which contain cards on which the randomization

assignment for each study participant is noted (the cards will be covered in aluminum foil inside the envelopes to defeat "hot-lighting" the envelopes). A copy of the randomization list will be given to a DOR investigator who is not affiliated with the ACCESS study, as backup in case the randomization envelopes are misplaced or stolen, and as validation for any study audits.

The randomization envelopes will be stored in a locked box that will be stored in a locked cabinet in the pre-op area, accessible only to appropriate study personnel. As noted above, randomization will occur in the pre-operative area prior to the participant being transported to the operating room for their surgery.

3.4 REFUSAL/REJECT LOG

A log of potential participants who decline to enter the study or who are deemed ineligible by the application of entry inclusion and exclusion criteria will be kept in order to judge the representativeness of those who consent to be randomized, consistent with CONSORT guidelines (20). If the individual and the IRB permits, data collected in the refusal/reject log will include the individual's age, gender, race/ethnicity, NRS pain score, and reason for rejection or refusal.

3.5 RECRUITMENT

3.5.1 CLINICAL PERSONNEL AND SITE

Participants will initially be recruited from [name] TKA patient list at KPNC San Leandro. If recruitment lags behind *a priori* goals, it will be expanded to include the TKA patients of other San Leandro orthopedists (Drs. [name] and [name] have agreed to complete their research trainings and participate in patient recruitment should [name] patients be insufficient to maintain recruitment at the required levels). KPNC San Leandro will remain the only clinical site; no patients will be recruited from any other KPNC facility.

3.5.2 RECRUITMENT STRATEGY AND MECHANISM

Patients will first be notified of the existence of the study by [name] (or another participating orthopedic surgeon) at their first clinic visit. After it has been determined that TKA is indicated and the patient is intending to undergo surgery, the orthopedist will briefly introduce the study to the patient. Unless the patient expresses clear disinterest in participating in the trial, they will be given an ACCESS clinic introductory packet by the clinic Patient Navigator along with their usual pre-operative preparation materials. This packet will contain the following items: informational materials about the ACCESS trial, two copies of the unsigned consent form, two copies of the unsigned HIPAA authorization form, one copy of the Research Subject's Bill of Rights, the baseline questionnaire, and a postage-paid reply envelope. An appointment will be made with the study Physician's Assistant for a telephone information-and-consent call with the patient.

3.6 PARTICIPANT COMPENSATION

Participants will be compensated \$50 for completing all study procedures including all pre-randomization activities, proceeding through randomization, and completing their post-operative data collection including the pain/medication diary and study-related telephone calls. Payment will be made in the form of a gift card to a commercial retail store (typically Target, Safeway, or Amazon).

4.0 MEASUREMENTS

4.1 PRIMARY OUTCOME

The primary outcome measurement for this study is the Numerical Rating Scale for pain recorded on the second postoperative day. The pain NRS is a 0-to-10 ordinal scale (with anchors, 0 = "no pain" and 10 = "worst possible pain") which the participant selects in response to the prompt, "What number best describes your typical pain in the past 24 hours?". Several different variations of pain-intensity measures exist but there is good evidence that numerical rating scales are easy to administer

with high respondent acceptability, high reliability (21,22), excellent validity when compared to visual analogue scales (21) and widely recommended as a core measure in pain trials (23).

The primary outcome will be obtained by the study Research Assistant via a telephone call on the second postoperative day. If the Research Assistant is unable to reach the participant by phone, the pain NRS score for the second postoperative day on the daily diary will be used for this measurement, if the diary is returned to the DOR.

4.2 SECONDARY OUTCOMES

Originally, the secondary outcomes included the PROMIS Global Health-10 short form and the Knee injury and Osteoarthritis Outcome Score short form (KOOS Jr). However, after further reflection among the study investigators, it was decided that these measures of symptoms and functions provided little meaningful outcome data among a sample of patients soon after knee replacement. Therefore, these measures were discarded as secondary outcome measurements.

However, the investigators decided that consumption of opioid medication in the 15 days postoperatively (as provided in the postoperative pain-and-medication diary) provided an important and meaningful secondary outcome measure for assessing the analgesic effectiveness of the ACC. The main secondary outcome measure will be the total number of 5mg oxycodone tablets (provided to all patients on discharge) consumed over the 15-day postoperative period. This change is reflected in the study schema, above.

4.3 OTHER MEASUREMENTS

In addition to these instruments, we will also collect data on patient demographics, clinical history of knee pain (approximate length of time with symptoms, prior interventions, history of ipsilateral knee trauma, etc.), prior medication use, and relevant comorbidities (e.g., gout, inflammatory arthritis).

5.0 INTERVENTIONS

5.1.1 ACTIVE AND CONTROL CONDITIONS

Participants in the intervention arm will have implanted a bupivacaine-filled ACC immediately prior to surgery, according to usual preoperative-care practices (for the patients of those orthopedists who use the catheters). As a pragmatic trial, there will be no change in the nature of the device or the manner in which it is implanted and managed postoperatively. All other aspects of pre-surgical, operative, and post-operative care will be conducted as per usual clinical practice.

Participants in the control arm will receive identical clinical care with the exception that no ACC will be placed in their leg prior to surgery.

5.1 STUDY DEVICE

The adductor canal catheter is a device which is placed by a trained anesthesia provider in order to apply analgesia to the anterior portion of the knee. It consists of a catheter, tubing and an adjustable time-release pump and reservoir. The reservoir is filled with 450 ccs of 0.2% ropivacaine. The catheter is inserted into the adductor canal, which contains the purely sensory saphenous nerve - a branch of the femoral nerve which supplies the anterior portion of the knee. The pump releases the ropivacaine in a controlled release fashion over 48-72 hours depending on the adjustable rate of the pump. When the reservoir is empty, the catheter is removed by the patient and disposed.

5.1.3 SOURCE AND MANAGEMENT OF DEVICE

The ACC is an FDA-approved medical device in current use within KPNC. The device is considered a standard-of-care instrument and, therefore, does not require special handling for use in a research study. The ACCs used for this study will be stored in the usual hospital locations and be filled with the bupivacaine anesthetic by the hospital pharmacist, in the usual manner. The device will be placed in the legs of the intervention-allocated patients by a KPNC anesthesiologist according to usual clinical practice and it will be removed by the patient by postoperative day three, according to the manufacturer's instructions. The device will be discarded by the patient at home and not be returned for study purposes.

5.1.4 CONCOMITANT MEDICATIONS AND RESTRICTIONS

All patients will receive periarticular anesthetic injections at the time of surgery. Postoperatively, all patients will receive a standard set of oral analgesic medications for pain control. These medications include ibuprofen 600 mg orally every 8 hours, acetaminophen 1 gm orally every 8 hours and oxycodone 5 mg 1 tab orally every 6 hours as needed for moderate pain or 2 tabs orally every 6 hours as needed for severe pain not relieved by other analgesics (patients also receive aspirin 81 mg orally twice daily for venous thromboembolism prophylaxis). Use of analgesic medications in the two weeks after surgery will be reported by the patient through the use of the daily patient diary (for those patients who are not discharged to home on the same day of surgery, we will also obtain data on the analgesic medications given to the patient while in the hospital). As a pragmatic trial, patients are free to use any recommended postoperative services, such as physical therapy in mind-body techniques for pain management.

5.1.6 ADHERENCE MEASURES

Because placement of the ACC will be carried out immediately after randomization by the attending anesthesiologist (for those participants randomized to receive an ACC), there is little opportunity for intervention non-adherence. However, It is anticipated there may be an occasional patient who develops "cold feet" immediately after randomization and declines the randomized assignment); these patients are randomized and will be asked to follow through with all other study - related procedures, including data collection. As the primary analysis will be intention-to-treat, participants will be analyzed in the group to which they were originally randomized, regardless of their actual adherence to the intervention.

Most data collection will occur in the two postoperative weeks. Both the baseline and closeout questionnaires will be administered over the phone, to help ensure completeness of data collection. All participants will be asked to complete a daily pain and medication diary which they will return to the Division of Research, where their data will be entered into a REDCap database with full range and logic checking. All patients will be called two days after surgery (for collection of the primary pain NRS outcome measurement), one week after surgery to encourage adherence with data collection, and again 14 days after surgery for completion of the closeout questionnaire and a reminder to return the daily diary to the DOR. Regular reports of the completeness of data collection will be generated and reviewed by all study personnel on a regular basis to ensure high quality of data collection. Any evidence of problems in data collection or quality will be addressed quickly and monitored carefully.

6.0 STUDY PROCEDURES

6.1 INITIAL CONTACT

Patients' first introduction to the ACCESS study will occur during their first visit with their orthopedist during which the decision regarding proceeding to TKA will occur. Using an IRB-approved script, the orthopedist will briefly describe the rationale and essential details of the study. The patient will be encouraged to ask questions and, if the patient expresses interest in learning more about the study, the orthopedist will inform the Patient Navigator.

After the patient's visit with their orthopedist, the Patient Navigator will hand to the patient a packet containing: informational materials about the ACCESS trial, two copies of the unsigned consent form, two copies of the unsigned HIPAA authorization form, one copy of the Research Subject's Bill of Rights, the baseline questionnaire, and a postage-paid reply envelope. An appointment will be made with the study Physician's Assistant for a telephone information-and-consent call with the patient.

6.2 TELEPHONE SCREENING AND CONSENT CALL

At the appointed time, the study PA will call the patient at home and present the study details to the patient using an IRB-approved script and answer any questions the patient may have. If the patient expresses a desire to enroll in the study, the PA will ask the patient to retrieve the consent and HIPAA Authorization forms from the clinic study packet; the PA will then walk through all elements of the consent form with the patient, again using an IRB-approved telephone script. If, after this procedure, the patient is still interested in enrolling in the study, they will sign their copy of the consent form. The same procedure will then be repeated for the HIPAA authorization form. The PA will then ask the patient to put both sign forms in the postage-paid reply envelope and mail them back to the orthopedics department at the SLN Medical Center. The PA will document this call in the patient's medical record.

During this call and after the consent is obtained, the PA will also conduct an eligibility screen to ensure that the patient meets all inclusion and none of the exclusion criteria; these will be documented in the study screening form.

6.3 PREOP TELEPHONE CALL

Approximately one-week prior to the participants TKA surgery, the study Research Assistant will call the patient at home to ensure that they are still intending to follow through with all study procedures and to ensure they understand the details of their further participation, including the randomization immediately prior to surgery. If the patient has any questions, they will be referred to the DOR co-PI ([name]) for further discussions. If the patient expresses any reservations about their further involvement in the study, they will not be randomized. If the patient is fully intending to continue with the study, the RA will administer the baseline questionnaire over the phone before ending the call.

During this call, the RA will also conduct a repeat eligibility screen to ensure that the patient meets all inclusion and none of the exclusion criteria.

6.4 DAY OF SURGERY

On the day of surgery, all preoperative activities will proceed as usual for patients undergoing TKA at the SLN Medical Center. The orthopedic surgeon, when meeting with the patient prior to surgery, will confirm once more that the patient is intending to be randomized and participate in the study. Note that there will be no additional consent procedure (as advised by the regulatory specialist with the KPNC DOR Clinical Trials Unit).

At the time when an ACC would normally be placed by the anesthesiologist (if the patient was going to have an ACC placed), the orthopedist or study PA will obtain the next consecutive randomization envelope and open it, revealing to the patient and anesthesiologist the randomization assignment. If the participant is randomized to placement of the ACC, the anesthesiologist will proceed with ACC placement as usual. If the participant is randomized to non-placement of the ACC, no ACC will be inserted and the remaining preoperative activities will continue as usual.

After surgery (whether the participant will be discharged to home on the day of surgery or admitted to the hospital), the patient will be given a packet containing all instructions for further participation, their daily pain-and-medication diary, and the closeout questionnaire). They will be told to begin filling out their diary the following day.

6.5 2-DAY FOLLOW-UP TELEPHONE CALL

On the afternoon of the second postoperative day, the study Research Assistant will call the participant at home to obtain their numerical rating pain score for the primary study outcome. They will inquire of the patient if they have any questions regarding their further participation, ensure that the participant understands their research-related responsibilities, and encourage adherence with all data

collection. Note that this call is separate from any clinical telephone calls made to the participant from the orthopedics department.

6.6 1-WEEK FOLLOW-UP TELEPHONE CALL

One week following the date of surgery, the study Research Assistant will call the participant at home to ensure that they are continuing to fill out their daily participant diary, inquire about any potential adverse events, answer any questions, and remind the patient that there will be a closeout phone call in another week.

6.7 2-WEEK CLOSEOUT TELEPHONE CALL

Two weeks after the date of surgery, the study Research Assistant will call the participant at home and conduct the closeout interview. The RA will again inquire about any potential adverse events since the prior call (including follow-up of previously reported AEs), answer any questions, then conduct the closeout questionnaire interview. Towards the end of the call, the RA will then instruct the participant to place their daily diary into the postage-paid reply envelope and mail the envelope to the DOR as soon as possible.

6.8 24-WEEK DATA EXTRACTION

Approximately 24 weeks after surgery, the study programmer will extract relevant clinical information from Clarity, primarily for the purpose of assessment for evidence of SAE's between two and 24 weeks postoperatively. Any evidence of potential SAE's during this time will be investigated by the DOR co-PI and reported in accordance with regulatory requirements.

6.9 VISIT WINDOWS

The following lists the follow-up visit windows outside of which data collection will be considered a protocol deviation:

One-week preoperative telephone call: Ten days prior and four days following

2-day follow-up telephone call: No window

1-week follow-up telephone call: No data collection at this call

2-week closeout telephone call: Two days prior and three days following

24-week data extraction: Two months following the 24-week timepoint (data will be collected only for the period from surgery to 24 weeks postoperatively)

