1.3 STUDY DESIGN

This is a randomized, open-label, two-arm, parallel-comparison noninferiority clinical trial of usual care with an ACC placed preoperatively compared to usual care without an ACC among adult patients undergoing elective unilateral TKA at the KPNC San Leandro Medical Center (Figure).

All patients meeting eligibility criteria will be introduced to the study by the treating orthopedist and PI, [name], at the patient's first clinic visit. If the patient expresses interest in study participation, they will be consented over the phone by the clinic Physician's Assistant (PA). Baseline data will be obtained via a telephone call with the study Research Assistant 7-10 days prior to the date of surgery. Randomization will occur in the preoperative area immediately prior to surgery. Patients will keep a daily diary of their pain levels and analgesic medication use for two weeks postoperatively and will be called by the study Research Assistant on post-op day two and day 14. A single electronic

medical record (EMR) data extraction for adverse events (focusing on emergency department and inpatient visits) will be conducted at 30 days postoperatively.

The primary outcome is the absolute pain score on post-op day two, measured on an 11-point numerical rating scale; the noninferiority margin for this comparison is set *a priori* at 2.0 points. Secondary outcomes include the total amount of opioid consumed over the two-week post-op period, the overall pain scores over the two-week post-op period, and adverse events directly attributed to the ACC.

[figure not shown]

Figure: Study Design Schema

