Secondary Aim 1: The first secondary analysis is a comparison of the mean NRS pain scores between the two treatment groups over the two-week follow-up period. We will have up to 15 measurements per individual (daily pain scores over a two-week period including baseline measurement). We are primarily interested in whether the rate of change in NRS pain score over the two-week follow-up period differs between the two treatment groups. These analyses will be conducted with linear mixed-effects models (38,39) that include terms for the effects of time, study group and the group-by-time interaction which will serve as the primary statistical test of the study hypothesis. Subjects will be included as random effects, and the within-subject correlation will be modeled appropriately. The most appropriate error structure will be chosen by comparing model fit using Akaike's Information Criterion (40). The overall difference between two total response curves will be tested with likelihood-ratio tests. The predicted

(modeled) change in the outcome over the relevant follow-up period will be obtained from each model along with the associated standard errors from which 95% confidence intervals will be constructed.

Secondary Aim 2: The mean difference in two-week postoperative opioid use (measured in total morphine equivalents) between the two treatment groups will be compared with a two-sample t-test. A secondary analysis will be conducted with a multiple linear regression model with an indicator variable for treatment group (for which the test of $\beta_1=0$ will form the primary hypothesis test) and adjustment for baseline covariates, use of opioids at baseline, and baseline NRS pain score.

Secondary Aim 3: The frequencies of complications related to ACC will be summarized with proportions and associated exact 95% confidence intervals.

Secondary Aim 4: To identify candidate predictors of differential response to the ACC, we will consider including interaction terms between the treatment indicator and demographic variables and baseline pain NRS scores in the primary linear regression analysis.

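### An in-window closeout call before day 14 can cut the diary short and understate the summed opioid total, and section 4.2's 15-day period does not match the two-week diary

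*Combined protocol and SAP*

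**What the plan says.** **Diary.** Section 1.3 states: "Patients will keep a daily diary of their pain levels and analgesic medication use for two weeks postoperatively". Section 6.4 fixes the first day, the day after surgery: "They will be told to begin filling out their diary the following day". The intended entries are therefore postoperative days 1 to 14.

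**Closeout call.** Section 6.7 places it at two weeks: "Two weeks after the date of surgery, the study Research Assistant will call the participant at home and conduct the closeout interview". Section 6.9 allows a tolerance before the call counts as a deviation: "2-week closeout telephone call: Two days prior and three days following". Near the end of the call the research assistant is to "instruct the participant to place their daily diary into the postage-paid reply envelope and mail the envelope to the DOR as soon as possible". Section 5.1.6 also links the 14-day call to returning the diary.

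**Outcome period.** Section 4.2 makes the diary the source of the opioid outcome and defines it as "consumption of opioid medication in the 15 days postoperatively". Section 2.2 (objective 2) and section 8.2 (Secondary Aim 2) use a two-week period. For pain, Secondary Aim 1 in section 8.2 says: "We will have up to 15 measurements per individual (daily pain scores over a two-week period including baseline measurement".

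**Analysis.** Secondary Aim 2 compares two-week opioid totals with a two-sample t-test. Multiple imputation appears only in the paragraph on the primary analysis. No rule is given for an opioid total built from an incomplete diary.

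**The concern.** A sum over days is comparable between patients only if every patient contributes the same days. Here a patient can follow the protocol fully, be called on day 12, post the diary that day and return 12 of the 14 intended days. No other source is named for opioid use after discharge. The total then depends partly on when the telephone call was made. Because there is no missing-day rule, the analyst would either count the absent days as zero or have to decide what to do with a short total after seeing the data, in an open-label trial.

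The length of the outcome period is a separate matter and does not depend on early calls. A diary that starts on day 1 and is mailed at an on-time day-14 call holds 14 days, not the 15 in section 4.2. If the day of surgery is meant as the fifteenth day, it is not in the diary. Section 5.1.4 collects hospital analgesic data only for patients not discharged on the day of surgery.

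What is at stake is the main secondary outcome.

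**Working it through.** **Step 1: the plan's own count.** Section 8.2 gives up to 15 pain measurements including baseline. One baseline score plus diary days 1 to 14 is 1 + 14 = 15, so that figure reproduces. Baseline can supply a fifteenth pain score but not a fifteenth postoperative opioid count.

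**Step 2: days available by call day.** The window is day 14 − 2 = 12 to day 14 + 3 = 17. Assume the diary is mailed on the call day with that day's entry made.

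| Call day | Entries | Share of 14 days | Share of 15 days |
|---|---|---|---|
| 12 | 12 | 12/14 = 86% | 12/15 = 80% |
| 13 | 13 | 13/14 = 93% | 13/15 = 87% |
| 14 | 14 | 100% | 14/15 = 93% |
| 15 to 17 | 15 or more, if the diary has room | 100% | 100% |

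If the call-day entry has not been made before mailing, each count falls by one. A day-12 call then gives 11/14 = 79% or 11/15 = 73%.

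**Step 3: share of the opioid total lost by a patient who mails on day 12.** The documents give no daily use pattern, so three are assumed. Let use on day d be proportional to r^(d−1), and count absent days as zero. Over a period of D days the share lost is

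sum of r^(d−1) for d = 13 to D, divided by sum of r^(d−1) for d = 1 to D.

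- Flat use (r = 1): D = 14 gives 2/14 = 14.3%; D = 15 gives 3/15 = 20%.
- Falling 10% a day (r = 0.9): D = 14 gives 0.537/7.71 = 7.0%; D = 15 gives 0.765/7.94 = 9.6%.
- Falling 20% a day (r = 0.8): D = 14 gives 0.124/4.78 = 2.6%; D = 15 gives 0.168/4.82 = 3.5%.

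**Step 4: an on-time call judged against 15 days.** Only day 15 is absent. The loss is 1/15 = 6.7% with flat use, 0.229/7.94 = 2.9% at r = 0.9 and 0.044/4.82 = 0.9% at r = 0.8.

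**Step 5: trial level.** If a fraction f of patients mail on day 12 and the rest are complete, the mean 14-day total is understated by f times the loss in step 3. The documents do not give f. Taking f from 10% to 50% as an assumed range:

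- Flat use: 0.10 × 14.3% = 1.4% to 0.50 × 14.3% = 7.1%.
- Falling 10% a day: 0.7% to 3.5%.
- Falling 20% a day: 0.3% to 1.3%.

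**The case against.** The strongest reply is that truncation is inferred. The call is nominally at two weeks, and day 12 is only the edge of a tolerance. The wording on mailing is prompt rather than immediate. The diary is described as a two-week diary, and section 6.4 says patients receive a packet of instructions that is not reproduced here. A sensible patient called on day 12 might finish the diary before posting it. This stands: the loss is possible, not certain, and its frequency is unknown. It does not remove the gap, because no visible text asks for the last days to be completed first.

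Three stronger readings are tempting, and the documents do not support them.

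- **Bias between arms.** A reader might infer that the treatment comparison is biased. That would need call timing or late opioid use to differ by arm, and nothing in the documents shows that either does. Truncation unrelated to arm lowers both means and adds noise.
- **Damage to the pain analysis.** A reader might infer that Secondary Aim 1 suffers equally. Its linear mixed model accepts incomplete series, so one or two absent late scores cost little.
- **An error in section 8.2.** The 15 pain measurements there are consistent, as step 1 shows. The mismatch is confined to the opioid period in section 4.2.

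It is also fair to say that the 14- versus 15-day mismatch is a matter of definition that changing the call window would not cure. It is treated separately here for that reason.

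**Conclusion.** The point holds in limited form. Following the stated window and mailing instruction can produce an opioid total that omits up to two of 14 days, or three if the call-day entry is also unmade. For a patient who mails on day 12 with that day's entry made, the 14-day total is understated by about 14%, 7% or 3% under the three assumed patterns. For the trial mean, the assumed 10% to 50% of such patients gives roughly 0.3% to 7%. If the pattern and the share of early calls are the same in both arms, a true difference in means shrinks by that same proportion. These figures rest on the assumed use patterns, on mailing on the call day and on absent days being counted as zero.

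The 15-day period in section 4.2 is inconsistent with the diary and with sections 2.2 and 8.2 whatever the timing of the calls. The day-2 primary outcome is unaffected. The change is worth making because the exposed outcome is the main secondary one and the repair is cheap.

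**What to change.** 1. **Section 6.7 and the call script:** ask patients to mail the diary only after completing the day-14 entry, whatever day the call takes place.
2. **Section 4.2:** define the opioid outcome over postoperative days 1-14, to match sections 2.2 and 8.2. The pain count in section 8.2 needs no change.
3. **Section 8.2, Secondary Aim 2:** state that uncompleted diary days are missing, not zero, and name the method. One option is to extend the plan's multiple imputation to the daily opioid amounts and sum after imputation. For diaries already returned short, this rule is the main remedy left, and it should be fixed before the data are analyzed.

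Narrowing the call window to 0 to +3 days is optional. It would turn early calls into deviations and is not needed if item 1 is adopted.

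The cost is protocol wording and a sentence in the script, with some diaries arriving up to about two days later.
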